#### Study Medication

Participants will be randomized to receive either NAC (n=55) or matched placebo (n=55) in double-blind fashion. The dose of NAC will be 2400 mg per day (1200 mg taken twice per day as two 600 mg capsules). This dose was chosen due to its demonstrated tolerability and evidence of efficacy in prior studies (29, 30, 33, 35). Medication will be prepared and packaged by Pitt St. Pharmacy, which has been used previously by our research team. Medication will be provided in pharmacy grade bottles. Bottles of medication will use the Medication Event Monitoring System (MEMSCapTM). These caps are child resistant and record a timestamp when the bottle is opened. The MEMSCap system will be used to monitor medication adherence during the trial. The participant and investigator/research staff will remain blinded to medication/placebo condition. Medication for active participants will be stored in locked cabinets in the research space occupied by [name] (Roper Medical Office Building, [name]).

#### Weekly Study Visits, Follow-Up, and Unscheduled Visits

Participants will return to the clinic for brief weekly visits on Days 7, 14, 21, 28, 35, 42, 49 and 56. At the Day 56 study visit (Week 8, EOT visit), medication will be terminated and a urine sample will be collected to determine smoking status (via urinary cotinine) (39). Participants will be asked to return to the clinic for a 4-week post-treatment follow-up visit at Day 84 (Week 12). During weekly study visits, research staff will review morning report data, perform pill counts, and review data from the MEMSCaps in order to monitor medication adherence. Medication tolerability will be systematically assessed by research staff. Medical clinicians on this protocol will be contacted for consult if any potentially related adverse events are reported. Participants will be encouraged to contact study personnel at any time to address any immediate concerns regarding adverse events. If a participant experiences intolerable medication-related adverse events at any point during the study, a dose reduction to 600 mg twice per day (1200 mg per day) may be undertaken. If a participant is unable to tolerate the reduced doses, the medication will be discontinued, and the participant will continue to be tracked. In previous studies at MUSC using NAC, dose reduction or termination has been rare. In addition to medication assessments, additional self-report smoking assessments will be administered (e.g., craving, withdrawal, smoking satisfaction, cigarettes per day, etc.). Breath CO will be collected at weekly visits, and brief cessation counseling will be conducted. Urine samples will be collected at key time points (Screening, Days 0, 28, 56, and 84) in order to assess for pregnancy, drug use, and cotinine. As stated previously, remote visits may be completed in place of in-clinic weekly visits. Participants may be asked to return to the study office to complete an unscheduled visit. This visit will be utilized to troubleshoot technology issues, dispense medication, or resolve other unexpected issues that may occur. It is not anticipated that any supplemental data will be collected.

**Baseline Screening Assessments**

1. **Demographic Data, Locator Information, Smoking History, and General Health Assessment:** Basic demographics, including age, gender, race, and social history will be collected. Participants will complete a locator information form which will be used to contact participants to remind them of study visits. The research team will use several methods of contact to keep in touch with participants. We will ask them to provide us with phone numbers, e-mail addresses, current home and work addresses, and contact information of family and friends who may know how best to reach them. We will also have a Facebook account that we may use to contact participants. The research team will only use private messages to contact participants through Facebook. This information will be kept in a locked cabinet with the protected health information. Additionally, participants will be asked about their smoking history and general health (i.e., current and/or past medical or psychiatric issues, current anxiety, stressors, etc.) to determine eligibility for study procedures.
2. **Mini International Neuropsychiatric Interview for DSM-5 (MINI) (40) :** The MINI is a brief, structured interview designed to ascertain a current, past, or lifetime history of the major Axis I psychiatric disorders in DSM-5 and ICD-10 and current substance use disorders.
3. **Beck Depression Inventory (BDI) (41):** A self-report depression instrument validated in adolescents and adults. This will be used to monitor depression symptoms at every study visit.
4. **Urine Pregnancy Test:** This will be monitored among female participants to exclude from study participation. This will be conducted before urine drug screen. If the pregnancy test is positive, the urine drug screen will not be performed.
5. **Urine Drug Screen:** This will be used to test for common drugs of abuse (e.g., marijuana, cocaine, opioids).
6. **Fagerström Test for Nicotine Dependence (FTND) (42):** This is a self-rating questionnaire for nicotine dependence. FTND has good reliability, validity and internal consistency.
7. **Timeline Follow-Back (TLFB) (43):** The TLFB is a calendar-based instrument that measures daily amounts of drug and alcohol consumption for a specified period of time by patient self-report. Study personnel will administer this instrument. A 30-day calendar will be used at baseline to gather information related to amounts of drug, alcohol, and tobacco use in the past 30 days. The TLFB will also be administered to collect data on cigarettes per day during the active study period.
8. **Readiness to Quit Scale:** This will be assessed on a 10-point scale, ranging from 1 = not ready to quit to 10 = extremely ready to quit.
9. **Generalized Self-Efficacy Scale (GSES) (44) and Smoking Abstinence Self-Efficacy (45):** These self-report measures will be used to assess the participant's self-efficacy in general and specially with respect to their ability to resist temptations to smoking in certain settings.
10. **Stages of Change short form (46):** The Stages of Change short form will assess prior quit attempts in the past year lasting for at least 24 hours and whether participants intend to quit smoking within the next 30 days (preparation stage), within the next 6 months (contemplation stage), or are not thinking of quitting (pre-contemplation stage).
11. **The Distress Tolerance Scale (DTS) (47):** This questionnaire is a validated self-report which measures tolerance, appraisal, absorption, and regulation of emotional distress.
12. **Carbon Monoxide Breathalyzer (Bedfont):** Breath carbon monoxide (CO) will be collected at screening, during all study visits, and remotely during Days 1-6 to detect residual levels of carbon monoxide from recent cigarette use.
13. **Urinary Cotinine:** Cotinine is a metabolite of nicotine. Quantitative cotinine analysis and qualitative cotinine instant dipsticks will be conducted to validate smoking self-reports and breath CO.
14. **Vital Signs:** Blood pressure and pulse will be monitored to assess medical stability. Height and weight will also be collected.
15. **Questionnaire on Smoking Urges—Brief (QSU-B) (48):** Participants will complete this brief form detailing symptoms of nicotine craving. Participants will additionally complete visual analog ratings of current level of craving and maximum & average levels of craving over the last week.
16. **Minnesota Nicotine Withdrawal Scale (MNWS) (49):** The MNWS, a DSM IV-based instrument that assesses symptoms of nicotine withdrawal, will be used to track participants' nicotine withdrawal symptoms.

17. **Modified Cigarette Evaluation Questionnaire (mCEQ)** (50): The 12-item mCEQ assesses the reinforcing effects of smoking and contains 5 subscales (smoking satisfaction, psychological reward, enjoyment of respiratory tract sensations, craving relief, aversion).
18. **Wisconsin Predicting Patient's Relapse (WI-PREPARE)** (51): The WI-PREPARE is a 7-item scale that predicts relapse to smoking through assessment of nicotine physical dependence, environmental factors, and individual difference characteristics.
19. **UPPS-P Impulsive Behavior Scale: Short version (SUPPS-P)** (52): The SUPPS-S is a 4-point Likert scale, 20-item measure that characterizes impulsive behavior through 5 subscales.
20. **Positive and Negative Affect Scale (PANAS)** (53): This questionnaire is a self-report measure that assesses positive and negative affect through ratings on 20 adjectives (10 positive and 10 negative). Each item is rated on 5-point scale capturing affect over the past 24 hours. This assessment will also be administered at weekly clinic visits and during the three days of reinforced abstinence.

#### Randomization and Weekly Visit Assessments (Days 0, 7, 14, 21, 28, 35, 42, 49, 56, and 84)

1. **Medication Diary:** Participants will be asked to report adherence with the medication regimen through the morning report survey. These reports will be reviewed at each study visit.
2. **Vital Signs:** Blood pressure and pulse will be monitored at key time points to assess medical stability and monitor for any changes during study participation (Days 7, 28, 56 and 84). Weight will be collected at key time points (Days 28, 56, and 84).
3. **Adverse Events:** Participants will be asked about adverse events at each study visit. This will be done to assess the safety and tolerability of study medication and procedures.
4. **Concurrent Medications Form:** The use of other medications will be monitored and documented at each clinic visit for safety purposes, including medications with known smoking cessation efficacy.
5. **Urine Pregnancy Test:** This will be monitored among female participants to determine if they should be terminated from the study at any point.
6. **Beck Depression Inventory (BDI)**
7. **Urine Drug Screen** (Days 0, 28, and 56 only)
8. **Penetration of Blind Assessment:** Participants will be asked if they think they are receiving active study medication or placebo. The research assistant conducting the study visit will also document whether they think the participant is receiving active medication or placebo (Days 7, 28, 56 and 84 only).
9. **Positive and Negative Affect Scale (PANAS)**

#### Smoking Assessments (Training, Days 0, 7, 14, 21, 28, 35, 42, 49, 56, and 84)

1. **Cigarette/Alcohol/Drug Use Diary:** Participants will complete a daily diary (REDCap survey) of cigarettes per day, alcohol, and drug use during active medication treatment, which will be reviewed at each weekly visit. The TLFB will be administered to collect data only when morning report data are missing for that day.
2. **Questionnaire on Smoking Urges—Brief (QSU-B):** Participants will complete this brief form detailing symptoms of nicotine craving. Participants will additionally complete visual analog ratings of current level of craving and maximum & average levels of craving over the last week.
3. **Minnesota Nicotine Withdrawal Scale (MNWS):** The MNWS, a DSM IV-based instrument that assesses symptoms of nicotine withdrawal, will be used to track participants' nicotine withdrawal symptoms.
4. **Modified Cigarette Evaluation Questionnaire (mCEQ):** The 12-item mCEQ assesses the reinforcing effects of smoking and contains 5 subscales (smoking satisfaction, psychological reward, enjoyment of respiratory tract sensations, craving relief, aversion).
5. **Carbon Monoxide Breathalyzer (Bedfont)**
6. **Urinary Cotinine:** Instant urinary cotinine dipstick tests will be conducted at all study visits, while quantitative tests will be conducted on Days 7, 28, 56, and 84.
7. **Readiness and Confidence to Quit Scale (Day 0)**

#### Mobile Assessments

1. **Cigarette/Other substance use Diary**
2. **Questionnaire on Smoking Urges—Brief (QSU-B)**

3. **Minnesota Nicotine Withdrawal Scale (MNWS)**
4. **Modified Cigarette Evaluation Questionnaire (mCEQ)**
5. **Carbon Monoxide Breathalyzer (Bedfont)**

#### Compensation

Participants will be compensated \$40 for screening, \$20 for training, and \$20 for randomization. They will be compensated \$20 for each weekly study visit (7 visits), \$50 for the Day 56 end-of-treatment study visit, and \$50 for the 4-week post-treatment follow-up visit (Day 84; Week 12). Compensation will be delivered to participants contingent on abstinence from smoking on Days 1-3 (\$40 per day, \$120 total), and for completing mobile surveys during Days 1-6 (\$5 per survey; \$60 possible compensation). Participants will also be compensated \$1 per completed mobile morning report (\$64 possible), and \$30 for returning all study devices and accessories in working order. Participants may earn a total of \$594 for study participation. All compensation paid to participants will be made in cash and in-person to the participant enrolled; this includes participant's that may qualify for remote visits.

In the event a participant does not return equipment to the study staff or it is returned in poor condition, this will affect their bonus equipment return compensation by not receiving \$30.

If an Unscheduled Visit is required during study participation, the participant will be compensated \$10 a visit in return for the time and travel demands.

Respondent-Driven Sampling (RDS) will be used to enhance recruitment of the sample. The RDS sampling methodology is based on recruiting the eligible friends and acquaintances of each participant so that the sample "snowballs". Each eligible participant who is enrolled into the study, and agrees to take part in this recruitment assistance, will be given coupons to pass on to other potential participants. A referral will be instructed to call the study team for screening. If that person successfully completes a screening assessment and is enrolled in the study, the participant who referred them can redeem the coupon for \$20. Participation in this process is completely voluntary. Participants may earn more than the listed \$586 if they chose to participate in respondent driven sampling. An RDS follow-up contact may be utilized to remind participants, whom agreed to future contact, that they are still eligible to participate even if no longer enrolled in the study.

#### Statistical Analyses

Categorical clinical and demographic variables will be assessed by chi-square tests of independence, while continuous variables will be assessed using Student's *t*-test. In addition to baseline group differences, preliminary analysis of baseline characteristics with tobacco use outcomes of interest will examine significant correlates of abstinence in the study population. Characteristics found to be significantly associated with tobacco abstinence and relapse outcomes will be included as covariates in the initial stages of model development. The primary measure of interest will be the proportion of biochemically confirmed and self-reported 3-day abstinence (defined as twice per day breath CO measures of  $\leq 6$  ppm or a 75% reduction from the participant's averaged baseline and Day 0 CO samples). The proportion of participants achieving 3-day abstinence will be compared between NAC and placebo treatment groups using logistic regression models (Specific Aim #1). Secondarily, there is great interest in determining if those who achieved 3-day abstinence under NAC treatment were less likely to relapse over the course of eight weeks compared than those who achieved abstinence under placebo treatment (Specific Aim #2). Daily smoking diary data will be used in conjunction with weekly breath CO measures to determine if and when relapse to regular smoking returned during the eight weeks of treatment with the study drug. Based on recommendations for defining treatment failure, relapse will be defined as smoking during seven consecutive days or smoking at least once over two consecutive weeks (54). This definition will account for regular and irregular smoking over the course of the eight-week intervention phase. Cox proportional hazards models will be developed to assess the efficacy of NAC in prolonging abstinence and preventing relapse. Additionally, end of study 7-day point prevalence abstinence will be assessed through the proportion of self-reported and biochemically confirmed 7-day abstinence. Biochemical confirmation for end-of-study abstinence is defined as a negative daily breath CO measures ( $\leq 6$  ppm or 75% reduction from baseline) and a negative urine cotinine measure ( $<80$  ng/mL). The main effect of NAC versus placebo on the proportion of abstinent participants will be assessed using logistic regression models. All stated models will be computed both unadjusted and adjusted for significant covariates and confounders found in the preliminary analysis. All randomized participants will be included in the primary analysis (intent-to-treat; ITT) and participants will be deemed not-abstinent at any missed visit or missing CO measure (drop-out/loss-to-follow up included). In addition to the primary ITT analyses,

additional exploratory approaches (e.g., modified ITT models, per protocol analysis, and completer analysis) will be undertaken as indicated and a sensitivity analysis comparing these models to the ITT model will be completed.

**Power and Sample Size.** This study is largely focused on obtaining preliminary data to inform and power a larger randomized controlled trial to assess NAC for TUD. However, the proposed sample size (N=110) of this study will allow for adequate power to detect differences between treatment groups for the first two stated aims and hypotheses. This study is powered to assess the hypothesis that NAC, as compared to placebo, will promote greater abstinence from smoking during a 3-day quit attempt at the beginning of an eight week randomized controlled trial. In a pilot trial (N=16) investigating NAC as a cessation aid over three days of reinforced abstinence, [name] and colleagues (35) found that the majority of study participants given NAC achieved high rates of abstinence on the second and third days of reinforced abstinence (75% and 100%, respectively) following a target quit date. Conversely, those randomized to the placebo condition achieved lower rates of abstinence on the second and third days (12.5% and 25%, respectively). With a proposed sample size in the current study of 110 participants (55 randomized to each treatment assignment), this number will provide sufficient power (80%) with a type 1 error rate of 5% to detect abstinence rate differences of as low as 20% between those randomized to NAC versus placebo.

Following the initial 3-day reinforced quit attempt, relapse rates will be examined to determine if NAC aids in relapse prevention as compared to placebo. Detectable relapse rates and associated hazard ratios (HR) based on the proposed sample size (N=110) are shown below in Table 1 based on varying relapse rates among the placebo and NAC groups. Including all randomized participants and assuming 70-90% of those randomized to placebo will relapse throughout the duration of the study, we will be sufficiently powered to detect relapse rates as high as 46-73% in those randomized to NAC (HR=1.8-2.0). Secondarily, we will assess relapse prevention among only those participants who achieved initial abstinence during the initial 3-day period. Assuming 30% of those randomized to placebo and 50% of those randomized to NAC will attain initial abstinence (low initial abstinence); we will have adequate power to detect relapse rates as high as 34-62% (HR=2.4-2.9) in the NAC group (assuming 70-90% relapse in the placebo group). If we achieve 50% and 75% initial 3-day abstinence in the placebo and NAC groups (high initial abstinence), we will have adequate power to detect relapse rates as high as 41-69% (HR=2.3-2.9) in the NAC group.

Placebo Relapse Rate	All Randomized Participants		Participants who achieve three day abstinence (ABS)			
	N=110		Low 3 day ABS; n=45		High 3 day ABS; n=70	
	Detectable NAC Relapse Rates	HR	Detectable NAC Relapse Rates	HR	Detectable NAC Relapse Rates	HR
70%	46%	1.98	34%	2.91	41%	2.25
80%	58%	1.86	46%	2.60	54%	2.09
90%	73%	1.76	62%	2.36	69%	1.95

*Table 1. Detectable rates of relapse and associated hazard ratios (HR).*

Additionally, assuming a conservative study attrition rate of 20%, a randomized sample of 110 participants (88 study completers) will provide sufficient power to detect a 23-29% difference in end-of-treatment (Week 8) abstinence between the two groups (assuming 10-30% abstinence rate in the placebo group). Therefore, 110 randomized participants will provide sufficient power to detect treatment differences for the first two stated hypotheses, and will provide effect sizes and estimates of variability for end-of-treatment abstinence at eight weeks to power a larger randomized controlled trial.

We will aim to recruit 110 enrolled study participants to have sufficient power to detect between group differences, but will plan to increase enrollment (N=120 total participants) to account for data integrity issues in a small number of participants.

*Missing Data and Attrition.* In order to minimize missing data and study attrition, enhanced communication between research staff and participants will be emphasized. However, these methods do not ensure that all data will be collected and appropriate analysis methods will be employed to accommodate missing data. In keeping with the ITT principle, we will make every effort to continue assessments for the entire course of treatment, even among those who fail to adhere to randomized assignment or stop participating in the study assigned intervention.

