## **D. RESEARCH DESIGN AND METHODS (including data analysis)**

### Study Design

This study will assess NAC as both an initial cessation aid and relapse prevention aid. Interested individuals will receive a brief telephone screening to determine if they may be eligible to participate. They will then be scheduled for an initial assessment, consisting of informed consent, followed by completion of self-report questionnaires and semi-structured interviews to determine eligibility. If participants are eligible for the study, they will be asked to return for their training visit. At the training visit, participants will be given instructions on completing remote surveys and counseling in preparation for their target quit date (TQD). Participants will then return for their randomization visit (Day 0), which will occur within 30 days of screening. On Day 0, participants will be randomized to receive double-blind NAC or placebo for eight weeks. Urn randomization procedures will be used.

Participants will then be contingently reinforced for abstinence from smoking for three days while taking study medication. Following three days of reinforced abstinence, participants will complete the remaining 8-week treatment intervention. Medication will be terminated at the Week 8 end-of treatment (EOT) visit.

Participants will then return at Week 12 (Day 84) for 4-week post-treatment follow-up visit to assess smoking status. The study design is shown in Figure 1. If

participants have unexpected conflicts after randomization and cannot keep weekly visit schedule (i.e. transportation issues or visit activity during an extended holiday), then participants may be eligible to complete weekly visits remotely via telephone call. During remote visits, Participants will be called via phone and all protocol procedures will be completed with the exception of a CO sample. Biologic collection (i.e. urine sample) may be obtained with proper planning, the participant may be given the opportunity and supplies required to complete an offsite/at home urine collection should they be willing to follow the proper collection and storage of a sample. Participants will be assessed for AE's, medication compliance, and will complete emailed surveys all within the assigned visit window. A CO sample will be collected at the participants next in-clinic visit. This option will only be used as a last resort for uninterrupted study participation.

[figure not shown]

Figure 1. Study design

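### Covariates are picked by their significance with the trial's own outcomes, and neither the unadjusted nor the adjusted model is named as primary, so the claimed 5% error belongs to no particular test

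*Combined protocol and SAP*

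**What the plan says.** All of this is in Section D.

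- **Selection rule (Statistical Analyses).** Besides baseline comparisons between arms, a "preliminary analysis of baseline characteristics with tobacco use outcomes of interest will examine significant correlates of abstinence in the study population". What passes goes forward: "Characteristics found to be significantly associated with tobacco abstinence and relapse outcomes will be included as covariates in the initial stages of model development". There is no candidate list, no threshold, and no account of what follows the initial stages.
- **Two models (same section).** "All stated models will be computed both unadjusted and adjusted for significant covariates and confounders found in the preliminary analysis". How a confounder would be identified is not defined.
- **What is called primary.** The word is attached to the 3-day abstinence measure and to the analysis population: "All randomized participants will be included in the primary analysis (intent-to-treat; ITT"). It is never attached to one of the two models. For Aim 1 the abstinence proportion "will be compared between NAC and placebo treatment groups using logistic regression models", with no covariates named.
- **Error and power (Power and Sample Size).** For a planned total of 110, with 55 in each arm, the claim is that "this number will provide sufficient power (80%) with a type 1 error rate of 5% to detect abstinence rate differences of as low as 20" per cent.
- **Randomization (Study Design).** "Urn randomization procedures will be used". No balancing factors are named there or elsewhere.

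**The concern.** A 5% type 1 error is a property of one specified test. Here each aim yields two tests, and the covariates of the second are known only after the outcomes have been examined. If the two fall on opposite sides of p=0.05, the plan gives no rule for which result stands.

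Three things are at stake:

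- **Error rate.** It rises above 5% if whichever model is significant may carry the claim.
- **Power.** Screening in 110 people lets in some noise variables and misses some real predictors.
- **Estimand.** The unadjusted odds ratio is marginal and the adjusted one is conditional on the covariates, so they are different quantities. Aim 3 exists to supply effect sizes for a larger trial, and the plan does not say which of the two would be passed on.

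**Working it through.** **1. The plan's own figure.** Inputs: 55 per arm, 5% error (two-sided assumed, because sidedness is not stated), and the plan's low scenario of 30% v 50%. The pooled-variance power is Φ[(d − 1.96·SE0)/SE1], where:

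- d = 0.20
- SE0 = √(2·0.4·0.6/55) = 0.0934
- SE1 = √((0.3·0.7 + 0.5·0.5)/55) = 0.0915

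This gives Φ(0.185) = 57%, or 69% one-sided, so the stated 80% is not reproduced at these rates. That is a separate issue. Its use here is that 57% is the reference for an unadjusted analysis under a true 30% v 50%.

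**2. Assumptions the plan does not supply.** Candidates number 10, 20 or 40, as independent standard normals. A candidate is kept at p<0.05 against the outcome pooled over arms. Prognostic strength is log-odds 0.5 (moderate) or 0.8 (strong) per SD. The models are logistic with Wald tests.

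**3. Aim 1 under the null** (30% baseline rate, 20,000 simulated trials per row; Monte Carlo SE √(0.05·0.95/20,000) = 0.15 points). Rejection rates:

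| Candidates (prognostic) | Unadjusted | Screened | Either | Fixed in advance |
|---|---|---|---|---|
| 10 (none) | 5.1% | 5.1% | 5.5% | 5.1% |
| 20 (3 moderate) | 4.9% | 4.9% | 6.6% | 5.0% |
| 20 (4 strong) | 5.2% | 5.2% | 7.8% | 5.2% |
| 40 (4 strong) | 5.0% | 5.4% | 8.0% | 5.1% |

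The screened model stays near 5% because the screen ignores treatment and treatment is randomized. The excess comes from having two tests. Two independent tests would give 1 − 0.95² = 9.75%; these two are correlated and fall short of that. A second set of runs with the marginal rates held fixed gave 4.3-5.4% for the screened model and 5.5-6.8% for either.

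**4. Noise variables.** If none of 20 candidates is prognostic, 20 × 0.05 = 1.0 enters by chance (simulated 1.02). With three prognostic, 17 × 0.05 = 0.85 (simulated 0.83-0.86).

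**5. Aim 1 power near 30% v 50%:**

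| Setting | Unadjusted | Screened | Fixed | Fixed − screened |
|---|---|---|---|---|
| 20 candidates, none prognostic | 57% | 56% | 57% | 1 |
| 3 moderate, marginal rates held at 30/50 | 56% | 60% | 64% | 4 |
| stronger predictors, marginal rates held at 30/50 | 56% | 65% | 68% | 3 |
| 10 candidates, 2 moderate | 55% | 58% | 60% | 2 |
| 20 candidates, 3 moderate | 54% | 57% | 61% | 4 |
| 20 candidates, 4 strong | 50% | 62% | 67% | 5 |

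In the last three rows the marginal rates were not held at 30/50. Unadjusted power below 57% shows that the marginal difference there was somewhat under 20 points, so these rows should be read across, not down.

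**6. Disagreement.** P(models disagree) = 2·P(either) − P(unadjusted) − P(screened). With no prognostic covariate: 2(59.6) − 57.3 − 56.0 = 5.9%. With 20 candidates and 3 moderate: 2(62.3) − 53.9 − 57.3 = 13.4%. With marginal rates held at 30/50, the range over the settings tried is about 6-18%. The uncalibrated 4-strong row would give 2(66.9) − 49.8 − 62.2 = 21.8%, but at a smaller true effect.

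**7. Aim 2 (Cox model, 3-day abstainers, null).** Arm sizes follow the plan's scenarios: 28 + 17 and 41 + 28, with 80% relapse and 20 candidates (2,500 runs, Monte Carlo error about 1 point). The screened model alone rejects in 5.4-6.3% and either model in 6.8-9.0%. A fixed-covariate model rejects in 5.2-6.5%, so part of the excess is small-sample behaviour that pre-specification does not remove.

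**The case against.** **The plan never says that either model may count.** It says only that both are computed. This stands: 5.5-8% is a conditional figure, and with few non-prognostic candidates the excess is about half a point. What remains is that nothing in the plan excludes that use.

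**Screening is not itself the culprit.** A reader might infer that choosing covariates by outcome inflates the false-positive rate. The calculations do not support that for Aim 1, where the screened model holds near 5%. A reader might also infer that screening costs precision. Relative to no adjustment it gains power when real predictors exist (56% to 60%, or 56% to 65%). The loss is only relative to fixing the truly prognostic variables, which no trial knows with certainty.

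**The inputs are not the plan's.** This is correct. Baseline Screening Assessments numbers 20 instruments, but some could not serve as covariates (locator information, the pregnancy test) and others have several subscales. The plan does not say that 20 are screened. Nor can one say that the urn factors are left out of the models: the plan names none and is silent.

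**The study is preliminary.** The protocol describes its main purpose as gathering data for a larger trial, and Aim 3 is estimation. That lowers the stakes. But the power paragraph claims adequate power for Aims 1 and 2 and a 5% error. The exploratory label covers the modified ITT, per-protocol and completer analyses, not the unadjusted/adjusted pair.

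**Conclusion.** The point holds in a limited form. That covariates are selected on the outcome, and that no primary model is named, is plain from the text. The numerical consequence is modest and depends on the assumed candidate number, threshold and prognostic strength. For Aim 1 the error is about 5.5-8% if either model may support the claim, against about 5% for any one named model. The models conflict in about 6-18% of trials under a true 30% v 50%. Screening recovers about 2-5 points less power than fixing prognostic covariates in advance, and there is nothing to recover if none is prognostic. The main defect is that the plan does not say which model its 5% refers to, nor which effect estimate would inform the next trial. It should be corrected, but it does not undermine the trial.

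**What to change.** Before unblinding, amend the Statistical Analyses section to:

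1. Name one primary model per aim. It contains treatment, any factors used in the urn randomization (state them, or state that there were none), and a short fixed set already collected and expected to be prognostic, for example FTND, baseline cigarettes per day and averaged screening/Day 0 CO.
2. State that the 5% error, and the effect estimate passed to the next trial, refer to that model.
3. Report the unadjusted model as supportive.
4. Keep outcome-based and baseline-difference screening as exploratory only. For Aim 2, keep the fixed set very short, given the 45 to 70 participants expected.

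The cost is SAP wording; no new data, visits or participants are needed. The downside is a small loss of flexibility, and little or no power gain if the chosen covariates prove not to be prognostic. The documents give no evidence on how strongly the suggested three predict 3-day abstinence, so the study team should justify the choice.
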